4.1 General Statistical Considerations

All data collected for the dose finding phase (Phase 1) and the cohort-expansion phase (Phase 2) will be listed. Phase 2 data will be summarized by tumor type and overall (all subjects) if appropriate. All subjects from Phase 1 will be summarized as an independent cohort with all cancer types combined.

Descriptive statistics (mean, standard deviation [Std Dev], median, minimum [Min], and maximum [Max]) will be used for continuous variables; number and percentage of subjects will be used for discrete variables. For change-from-baseline calculations, the last measurement prior to the first dose of IMP will be used as the baseline value.

For summary statistics, the mean and median will be displayed to one decimal place greater than the original values; the standard deviation will be displayed to two decimal places greater than the original values.

All tabulations of summary statistics, graphical presentations, and statistical analyses will be performed using SAS[®] Version 9.4 or higher.

4.2 Determination of Sample Size

The sample size for the dose-finding phase of the study is based on a standard 3+3 dose-finding design and depends on observed toxicity. With 2 doses under consideration, a maximum of 12 subjects will be required.

The Simon's 2-stage optimal design is used for the expansion cohorts. A cohort may be considered for termination due to lack of efficacy if the observed number of tumor responses (either confirmed or unconfirmed) in the first stage is too small. The characteristics of this design depend on 2 probabilities: the false positive rate (FPR), the probability of declaring the experimental treatment to be superior when in fact it is no better than the historical standard, and the false negative rate (FNR), the probability of concluding the experimental treatment to be no better than the historical standard, when in fact it is superior. Table 1 below presents operating characteristics of the Simon's 2-stage design with 15% FPR and 10% FNR for various expansion cohorts and their historical and target objective response rates. For example, an initial evaluation of efficacy may be performed after 16 treated subjects with squamous cell NSCLC have evaluable tumor response data. Guided by the Futility Boundary as shown, the decision to terminate the cohort or to allow it to continue will be made after taking into consideration other relevant observations such as duration and depth of response and risk/benefit profile. The number of subjects receiving treatment at the time of the Stage 1 efficacy evaluation may exceed the specified Stage 1 sample size depending on accrual rate, response lag, and other factors.

Upon completion of Stage 1 enrollment for a given cohort, the safety review committee (SRC) will review available efficacy and safety data and determine whether enrollment into Stage 2 may continue, even if not all response data are yet available to determine whether the Stage 1 criteria have been met. The SRC may decide that enrollment may continue if the benefit risk assessment is perceived to be positive.

With FPR (or one-sided alpha) being 15% and FNR (or 1-power) being 10%, the following table shows sample size required for each tumor type.

Table 1 Sample Size Estimation by Tumor Type

Tumor Type	Response Assumption		Simon 2-Stage Sample Sizes ^a		Probability of Early Stopping due to Futility (%) if true response rate = Lower Bound
	Lower Bound Historical Response Rate (%)	Target Response Rate (%)	Stage 1 (n1)/ Total (N)	Stage 1 Response Futility Boundary (≤): Stop if this many responses or fewer	
NSCLC SQ	20	40	16/32	3	60
NSCLC NSQ PD-L1 non-expressing	10	30	10/21	0	35
Ovarian	10	30	10/21	0	35
CRC (non-MSI high)	5	20	12/29	0	54
SCCHN	25	45	14/36	3	52
HCC	16	36	12/28	1	41
Pancreatic	0	15	15/17	0	>99

a: False positive rate (FPR) or one-sided alpha=15% and false negative rate (FNR) or 1-power=10%.

CRC=colorectal carcinoma; n1=sample size in Stage 1; N=sample size; non-MSI high=non-microsatellite instability high; NSCLC=non-small-cell lung cancer; NSQ=non-squamous; PD-L1=programmed cell death-ligand 1; HCC=hepatocellular carcinoma; SCCHN=squamous cell carcinoma of the head and neck; SQ=squamous.

A maximum of 188 subjects will participate in the study. This number takes into account a total of 4 subjects that were enrolled in the dose-finding stage and a total of 184 subjects (across all tumor types) calculated for the expansion cohort.

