### **12.3.1 Sample Size Determination**

The sample size for the dose-finding phase of the study is based on a standard 3+3 dose-finding design and depends on observed toxicity. With 2 doses under consideration, a maximum of 12 subjects will be required.

The Simon's 2-stage optimal design will be used for the expansion cohorts. A cohort may be considered for termination due to lack of efficacy if the observed number of tumor responses (either confirmed or unconfirmed) in the first stage is too small. The characteristics of this design depend on 2 probabilities: the false positive rate (FPR), the probability of declaring the experimental treatment to be superior when in fact it is no better than the historical standard, and the false negative rate (FNR), the probability of concluding the experimental treatment to be no better than the historical standard, when in fact it is superior. The table below presents operating characteristics of the Simon's 2-stage design with 15% FPR and 10% FNR for various expansion cohorts and their historical and target objective response

rates. For example, an initial evaluation of efficacy may be performed after 16 treated subjects with squamous cell NSCLC have evaluable tumor response data. Guided by the Futility Boundary as shown, the decision to terminate the cohort or to allow it to continue will be made after taking into consideration other relevant observations such as duration and depth of response and risk/benefit profile. The number of subjects receiving treatment at the time of the Stage 1 efficacy evaluation may exceed the specified Stage 1 sample size depending on accrual rate, response lag, and other factors.

Upon completion of Stage 1 enrollment for a given cohort, the SRC will review available efficacy and safety data and determine whether enrollment into Stage 2 may continue, even if not all response data are yet available to determine whether the Stage 1 criteria have been met. The SRC may decide that enrollment may continue if the benefit risk assessment is perceived to be positive.

With FPR or one-sided alpha=15% and FNR or 1-power=10%.

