**Table 12.3.1-1 Sample Size Estimation by Tumor Type**

Tumor Type	Response Assumptions		Simon 2-Stage Sample Sizes a		Probability of Early Stopping due to Futility (%) if true response rate= Lower Bound
	Lower Bound Historical Response Rate (%)	Target Response Rate (%)	Stage 1 (n1)/Total N	Stage 1 Response Futility Boundary ( $\leq$ ): stop if this many responses or fewer	
NSCLC SQ	20	40	16/32	3	60
NSCLC NSQ PD-L1 non-expressing	10	30	10/21	0	35
Ovarian	10	30	10/21	0	35
CRC (non-MSI high)	5	20	12/29	0	54
SCCHN	25	45	14/36	3	52
HCC	16	36	12/28	6	41
Pancreatic	0	15	15/17	0	>99

a: False positive rate (FPR) or one-sided alpha=15% and false negative rate (FNR) or 1-power=10%.

CRC=colorectal carcinoma; n1=sample size in Stage 1; N=sample size; non-MSI high=non-microsatellite instability high; NSCLC=non-small-cell lung cancer; NSQ=non-squamous; PD-L1=programmed cell death-ligand 1; HCC=hepatocellular carcinoma; SOC=Standard of care; SCCHN=squamous cell carcinoma of the head and neck. SQ=squamous.

A maximum of 188 subjects will participate in the study.

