4 STATISTICAL METHODOLOGY

This plan describes methods planned for the analysis and display of efficacy, safety, pharmacokinetic parameters, and immunogenicity endpoints. Separate plans will document exploratory analyses of pharmacokinetic/pharmacodynamic data, pharmacodynamic relationships with safety and/or efficacy results, and the effects of immunogenicity on safety, efficacy, pharmacokinetic and pharmacodynamic.

The specific endpoints are as follows.

Primary Endpoints:

- Safety and tolerability will be evaluated by assessing adverse events (AEs), changes in physical examination findings, vital sign measurements, 12-lead electrocardiogram (ECG) readings, and clinical laboratory evaluations.

Secondary Endpoints:

- Overall response will be evaluated using RECIST v1.1. Overall response rate is calculated based on the best overall response (BOR), defined as the best response designation recorded between the date of first dose of investigational medical product (IMP) and the date of subsequent anti-cancer therapy (excluding on-treatment palliative radiotherapy of non-target bone or CNS lesions). Note: Continuation of nivolumab after discontinuing combination therapy does not count as start of new therapy for this definition. A BOR of either complete response (CR) or partial response (PR) requires confirmation of the assessment at least 4 weeks later. In addition, as a sensitivity analysis, BOR will also be defined as the best response designation recorded between the date of first dose of IMP and the date of first objectively documented progression (i.e. radiographic progression) or the date of subsequent anti-cancer therapy (excluding on-treatment palliative radiotherapy of non-target bone or CNS lesions), whichever occurs first.
- Time to response (TTR): Days from Cycle 1 Day 1 to the first assessment date of confirmed CR/PR using RECIST v1.1.
- Duration of response (DOR): Days from the first assessment date of confirmed CR/PR to the date of death or progressive disease (PD), whichever is earlier, using RECIST v1.1.

For subjects who neither progress nor die, the duration of objective response will be censored at the same time they will be censored for the primary definition of PFS. DOR will be evaluated for responders (i.e. subjects with confirmed CR or PR) only.

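### HCC Stage 1 boundary differs between protocol and SAP, and the 15%/10% error rates rest on unprinted final cut-offs, in five of seven cohorts on a binding Stage 1, and on benchmark rates the SAP leaves open

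*SAP*

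**What the plan says.** SAP 4.2 and Protocol 12.3.1 plan a Simon two-stage optimal design for each expansion cohort. The SAP introduces its Table 1 with "With FPR (or one-sided alpha) being 15% and FNR (or 1-power) being 10%, the following table shows sample size required for each tumor type", and footnote a repeats the pair, in percent: "False positive rate (FPR) or one-sided alpha=15% and false negative rate (FNR) or 1-power=10". Each table gives the historical and target rates, n1/N, the Stage 1 futility boundary and the probability of early stopping. Neither gives the number of responses out of N at which a cohort is declared active.

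The HCC rows differ. The protocol prints "HCC 16 36 12/28 6 41" and the SAP prints "HCC 16 36 12/28 1 41"; the fourth figure is the Stage 1 boundary.

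The boundary is guidance only. In SAP 4.2, "the decision to terminate the cohort or to allow it to continue will be made after taking into consideration other relevant observations", and Protocol 12.3.1 says the same. On timing, the SRC may rule that "enrollment into Stage 2 may continue, even if not all response data are yet available to determine whether the Stage 1 criteria have been met".

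Stage 1 counts responses loosely: a cohort may be considered for termination "if the observed number of tumor responses (either confirmed or unconfirmed) in the first stage is too small". The final ORR is stricter, because it is built on BOR: "A BOR of either complete response (CR) or partial response (PR) requires confirmation of the assessment at least 4 weeks later".

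Protocol 12.3.2 sets a general one-sided 0.15 level without naming an ORR test or a count. SAP 4.9.1 plans the ORR with an exact two-sided 95% confidence interval. SAP 4.9.2.2 closes by saying that the assumed historic and target rates may have changed and may need adjusting by the time the data are evaluated.

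**The concern.** A false positive rate is the probability of a declaration, so it has a value only once the count that triggers the declaration is fixed. Here that count is missing, the interim rule assumed in the calculation is optional, and the benchmark can move after responses are visible. A reader could therefore take 15%/10% as a property of the written plan when it belongs to a stricter rule that the plan does not state.

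For HCC the two documents give thresholds with very different consequences for the same cohort. At stake is the secondary conclusion on anti-tumor activity. The primary safety and tolerability analysis does not depend on any of this.

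**Working it through.** **Inputs.** p0 (historical rate), p1 (target rate), n1, N and r1 (Stage 1 boundary) come from SAP Table 1; the limits are false positive rate (FPR) ≤ 15% and power ≥ 90%. X1 is the Stage 1 response count, X the count out of N, and r the largest final count that is not a success.

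**Formulas (exact binomial).**
- Early stopping: P(X1 ≤ r1 | n1, p0).
- Stage 1 binding: P(X1 > r1 and X > r), at p0 for FPR and at p1 for power.
- Stage 1 never enforced: P(X > r | N), at p0 and at p1.

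**Step 1: the plan's own figures.** A search for the Simon optimal design under these limits returns the SAP's n1, N and r1 for SQ, NSQ, ovarian, CRC, SCCHN and HCC. Early stopping is 59.8%, 34.9%, 34.9%, 54.0%, 52.1% and 40.6%, against 60, 35, 35, 54, 52 and 41 printed. The N sum to 32 + 21 + 21 + 29 + 36 + 28 + 17 = 184, as stated.

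**Step 2: HCC boundary (n1 = 12).**
- Boundary 1, true rate 16%: 0.84^12 + 12 × 0.16 × 0.84^11 = 0.1234 + 0.2821 = 0.4055, which is the printed 41%. At 36% it is 0.0366.
- Boundary 6: P(X1 ≤ 6) = 0.9990 at 16% and 0.9030 at 36%. If the boundary is followed, power cannot exceed 1 − 0.9030 = 0.0970.

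**Step 3: final cut-offs.** Scanning every r with n1, r1 and N held at the SAP values and Stage 1 binding leaves exactly one cut-off per cohort that meets both limits. The last two columns use the same cut-off with Stage 1 never enforced.

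| Cohort | Success if at least | FPR, binding | Power, binding | FPR, not enforced | Power, not enforced |
|---|---|---|---|---|---|
| SQ | 9/32 | 0.1480 | 0.9031 | 0.1746 | 0.9425 |
| NSQ, ovarian (each) | 4/21 | 0.1455 | 0.9022 | 0.1520 | 0.9144 |
| CRC | 3/29 | 0.1480 | 0.9005 | 0.1751 | 0.9480 |
| SCCHN | 12/36 | 0.1430 | 0.9014 | 0.1671 | 0.9440 |
| HCC (boundary 1) | 7/28 | 0.1388 | 0.9053 | 0.1487 | 0.9243 |

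The choice of count matters. With Stage 1 binding, a cut-off one response lower gives FPR of 22% to 32% across these cohorts; one response higher gives power of 80% to 86%.

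**Step 4: Stage 1 not enforced.** No cut-off meets both limits for SQ, NSQ, ovarian, CRC or SCCHN. For example, SQ at ≥ 9 has FPR 0.1746, and at ≥ 10 has FPR 0.0898 but power 0.8844. HCC at ≥ 7 still meets both.

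**Step 5: pancreatic (p0 = 0, p1 = 15%, 15/17, boundary 0).** With success at one or more responses, power is 1 − 0.85^15 = 0.9126 (binding) or 1 − 0.85^17 = 0.9369 (not enforced). FPR is 0 if the true rate is exactly 0. At an assumed true rate of 1% it is 1 − 0.99^15 = 0.140 (binding) or 1 − 0.99^17 = 0.157 (not enforced).

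**Step 6: benchmark.** The documents give no size for any adjustment. As an illustration only, assume that the true null rate is 5 points above the printed one, with the same cut-off and Stage 1 binding. FPR is then 35.5% (SQ), 37.5% (NSQ, ovarian), 49.8% (CRC), 34.3% (SCCHN) and 35.1% (HCC). The meaning of a given count depends strongly on which rate is used.

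**The case against.** The strongest reply is that ORR is a secondary endpoint, reported as an estimate with a confidence interval in a study evaluated mainly by listings and summaries, so no formal success rule is owed. The cut-offs can also be recovered uniquely from the printed values, and the SAP says that it supersedes the protocol on analysis details. Part of this stands. The omission is repairable and the design itself is sound. But both documents state error rates for a declaration of superiority, and a count that a reader can derive is not one that the plan has fixed. The SAP also undertakes to identify substantial differences from the protocol, and SAP 4.2 flags none for HCC. The protocol's 6 happens to equal the derived final r for HCC, but it is printed as a Stage 1 boundary.

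Several stronger readings are tempting and are not supported:
- That 15%/10% fails in every cohort once Stage 1 is advisory. HCC (14.9%, power 92.4%) and pancreatic (0% at the printed historical rate, power 93.7%) keep both limits.
- That the 10% false negative rate is in danger. Not enforcing a futility boundary raises power.
- That the response definition for the final count is open. Protocol 10.1 and 12.3 and SAP 4 and 4.9.1 together define ORR on confirmed BOR. What differs is Stage 1, which also accepts unconfirmed responses.
- That HCC power is capped at 9.7% as the protocol stands. The cap applies only if the boundary of 6 is followed, and the protocol does not require that.
- That the 15% is wrong for pancreatic. It is a ceiling, and 0 lies below it; it simply does not describe that row.

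A benchmark that has become outdated is a genuine problem, so wishing to update it is reasonable. The difficulty is that the SAP gives no procedure or cut-off date, in a trial where responses are visible as they accrue.

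**Conclusion.** The point holds in four parts. The HCC Stage 1 boundary contradicts itself across the documents, and only 1 agrees with the 41% printed in both. The stated error rates require one unprinted final cut-off per cohort. Because Stage 1 is advisory, the 15% is not guaranteed in SQ, NSQ, ovarian, CRC and SCCHN: the worst case is 17.5% (SQ, CRC), 16.7% (SCCHN) and 15.2% (NSQ, ovarian), an excess of at most 2.5 points, with power of 91% to 95%. The benchmark is not fixed before responses are seen.

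The worst case assumes that every failed boundary is overridden; partial adherence lies between the binding and unenforced figures. All figures assume the planned N, although Phase 2 subjects may be replaced, and one response definition at both stages. The consequence is confined to the secondary activity conclusion.

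**What to change.** 1. Reconcile the HCC Stage 1 boundary between Protocol Table 12.3.1-1 and SAP Table 1; 1 is the value that matches the printed 41%.
2. Add a final cut-off column to both tables: 9/32 (SQ), 4/21 (NSQ), 4/21 (ovarian), 3/29 (CRC), 12/36 (SCCHN), 7/28 (HCC), applied to confirmed BOR. State that the error rates assume planned N and one response definition at both stages, whereas Stage 1 also counts unconfirmed responses. Label the cut-offs post hoc if they are added after responses have been seen. The SAP's shell for Table 14.2.3.1 already refers to a limited number of responders, so this label may well be needed.
3. Extend footnote a for SQ, NSQ, ovarian, CRC and SCCHN only: the 15% assumes a binding Stage 1, and if it is not enforced the FPR is up to 17.5%, 15.2%, 15.2%, 17.5% and 16.7% respectively.
4. Replace the last sentence of SAP 4.9.2.2 so that decisions use the Table 1 rates and any updated rate appears as a supportive comparison only.
5. Add a note to the pancreatic row that the 15% is a ceiling that does not describe it. Give power at the 15% target for one or more responses (91.3% binding, 93.7% not enforced), and state that FPR is 0 only at a true rate of exactly 0.

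The cost is table and wording changes in two documents; n1, N, the SAP's Stage 1 boundaries and the 184 and 188 totals stay. The downside is that the stated FPR looks slightly less favourable, and an updated literature rate can no longer drive a decision.

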## **6 DESCRIPTION OF STUDY DESIGN AND POPULATION**

### **6.1 Study Overview**

This is a multicenter, Phase 1/2, open-label, dose-finding and cohort-expansion study of the anti-CCR4 antibody mogamulizumab in combination therapy with the anti-PD-1 antibody nivolumab in adult subjects with locally advanced or metastatic solid tumors. Subjects will be screened for entry into this study after signing the informed consent form (ICF). Subjects who meet study entry criteria will enter the treatment cohort that is open to enrollment.

The study includes a Phase 1 dose finding and a Phase 2 cohort-expansion:

- Phase 1 dose-finding has a 3+3 design that will identify the MTD, or the highest protocol-defined dose in the absence of exceeding the MTD, for the combination regimen and will enroll up to 12 subjects (3 to 6 subjects per cohort).
- Phase 2 cohort-expansion will explore the safety, PK, PD, and anti-tumor activity of the highest tolerated dose of the combination regimen and will enroll up to 184 subjects (21 to 36 per cohort) in up to 7 tumor-specific expansion cohorts.

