### **12.3.2 Significance Level**

Statistical tests will use a 0.15 significance level and will be 1-sided unless otherwise noted. Confidence intervals will be at 95% confidence level unless stated otherwise.

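### The pancreatic row (null 0%, 15/17, stop at 0) does not have the 15% false positive rate its footnote gives it, lacks a final rule, and has N=17, below the stated 21 to 36 per cohort

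*SAP*

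**What the plan says.** The row is the same in SAP 4.2 Table 1 and Protocol Table 12.3.1-1: "Pancreatic 0 15 15/17 0 >99". In column order that is a historical rate of 0%, a target of 15%, Stage 1 of 15 within a total of 17, a futility boundary of 0 responses, and an early-stopping probability above 99% under the null. The footnote to both tables applies to every row: "False positive rate (FPR) or one-sided alpha=15% and false negative rate (FNR) or 1-power=10" (per cent).

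On the method, SAP 4.2 says "The Simon's 2-stage optimal design is used for the expansion cohorts" and defines the FPR as "the probability of declaring the experimental treatment to be superior when in fact it is no better than the historical standard". Protocol 12.3.2 adds: "Statistical tests will use a 0.15 significance level and will be 1-sided unless otherwise noted". Neither document prints a final (Stage 2) boundary for any cohort.

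The Stage 1 rule is guidance. SAP 4.2 makes a cohort a candidate for stopping when "the observed number of tumor responses (either confirmed or unconfirmed) in the first stage is too small", but also says: "The SRC may decide that enrollment may continue if the benefit risk assessment is perceived to be positive".

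On size, Protocol 6.1 says the expansion phase "will enroll up to 184 subjects (21 to 36 per cohort) in up to 7 tumor-specific expansion cohorts". The same 21 to 36 range stands in the protocol synopsis (Study Design, Phase 2: Cohort expansion, and Number of Subjects), in Protocol 6.1.3, and in SAP section 3.

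**The concern.** A two-stage Simon design is described by two error rates and two boundaries. Here the null is exactly 0%, so a single response contradicts it with certainty and there is no false positive rate to control. A reader of the table is nevertheless told that this cohort has the same 15% control as the other six. The real chance of passing an inactive combination depends on how far the true background rate lies above zero, and the table does not show that.

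The final boundary is also missing, so the reader cannot tell what Stage 2 adds. A Stage 2 of only two subjects, after a Stage 1 that needs one response, suggests a single-stage screen set out as a two-stage design. Finally, a planned size of 17 cannot fall in a range that starts at 21.

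**Working it through.** **Inputs.** From SAP Table 1 and Protocol Table 12.3.1-1: p0 = 0, p1 = 0.15, n1 = 15, N = 17, r1 = 0 (stop at 0 responses), FPR limit 15%, FNR limit 10%. All probabilities are exact binomial.

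**1. Reproduce the row.** With r1 = 0, power cannot exceed 1 − 0.85^n1.
- n1 = 14: 1 − 0.85^14 = 0.897, below 0.90.
- n1 = 15: 1 − 0.85^15 = 0.9126, at or above 0.90.

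So n1 = 15 and r1 = 0 reproduce. Early stopping at p0 = 0 is (1 − 0)^15 = 100%, consistent with the printed entry above 99%. A full search for the optimal design returns N = 16 rather than 17. At p0 = 0, however, the expected size is 15 + 0 × (N − 15) = 15 for every N, with FPR 0 and power 0.9126 throughout, so N is arbitrary. The same search returns the other six SAP rows exactly (HCC with the SAP's Stage 1 boundary of 1), with attained FPRs from 13.9% to 14.8%. The 15% limit therefore works as intended everywhere except here.

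**2. Attained FPR.** At p0 = 0, P(at least 1 response) = 1 − 1^15 = 0. This holds for any rule that needs at least one response.

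**3. Which final rule fits the stated FNR?** Power at 15%, given at least 1 response in Stage 1:
- Final rule at least 1: 1 − 0.85^15 = 91.3%.
- Final rule at least 2 of 17: P(X1 ≥ 2) + P(X1 = 1) × P(X2 ≥ 1). P(X1 = 0) = 0.0874 and P(X1 = 1) = 15 × 0.15 × 0.85^14 = 0.2312, so P(X1 ≥ 2) = 0.6814. P(X2 ≥ 1) = 1 − 0.85^2 = 0.2775. Total: 0.6814 + 0.2312 × 0.2775 = 74.6%.
- Final rule at least 3 of 17: 48.0%.

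Only at least 1 response meets the 10% FNR. Under it, a cohort that passes Stage 1 has already met the final criterion, so two-stage power equals single-stage power at n = 15.

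**4. Chance of passing at a non-zero background rate.** The rates of 1%, 2% and 5% are assumptions; the documents give only 0%.

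| True rate | Stage 1 followed: 1 − (1 − p)^15 | All 17 enrolled regardless: 1 − (1 − p)^17 |
|---|---|---|
| 1% | 14.0% | 15.7% |
| 2% | 26.1% | 29.1% |
| 5% | 53.7% | 58.2% |
| 15% (target) | 91.3% | 93.7% |

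With Stage 1 followed, the chance of passing exceeds 15% once p > 1 − 0.85^(1/15) = 1.08%. Early stopping stays above 99% only while p < 1 − 0.99^(1/15) = 0.067%.

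**5. Cohort size.** 32 + 21 + 21 + 29 + 36 + 28 + 17 = 184, the stated Phase 2 total. With 21 for pancreatic, Phase 2 would be 188, and with the 4 Phase 1 subjects the study would be 192, against a stated maximum of 188.

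**The case against.** The best defence is that 15% and 10% are design ceilings. An attained FPR of 0 and a power of 91.3% satisfy both, and no figure printed in the row is wrong. That is so: the figures reproduce. What fails is the footnote as a description of the row, because it equates the FPR with one-sided alpha at 15% and a reader will take the cohort to carry that risk.

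The second defence concerns Stage 2. A reader might infer that subjects 16 and 17 can never affect the decision, or that treating them serves nothing. The documents do not support either reading. No final boundary is printed, and Stage 1 is non-binding. If the Safety Review Committee (SRC) let the cohort continue after 0 of 15, the last two could supply the first response. They also contribute to the safety, PK and PD aims in Protocol 6.1 and to the precision of the response rate.

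A reader might also infer that the row gives no protection at a background rate of 1 to 2%. The figures contradict this. With Stage 1 followed, the 1% case passes 14.0% of the time, inside the 15% limit, and at 2% the cohort still stops about 74% of the time.

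Nor do the documents show that one response would formally be declared superiority. Safety is the primary endpoint, the response rate is reported with an exact 95% interval (SAP 4.9.1), and no SAP table lists a test against the historical rate.

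Finally, the rationale for the pancreatic cohort (Protocol 4.5.7) is redacted, so whether 0% was justified cannot be judged. SAP 4.9.2.2 also allows the historical rates to be revised by the time of evaluation. This cuts the other way too: any upward revision gives the row a non-zero FPR.

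**Conclusion.** The point holds in three parts.

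- The 15% FPR does not describe the pancreatic row. At the stated null the attained FPR is 0. At non-zero background rates it depends on the rate, and with Stage 1 followed it exceeds 15% above about 1.1%.
- The final rule is missing. The stated FNR implies at least 1 response. Under that rule, and if the Stage 1 boundary is followed, subjects 16 and 17 do not decide efficacy.
- The planned 17 contradicts 21 to 36 wherever that range appears. The 184 total is correct and already uses 17, so the range is what needs changing.

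The pass probabilities rest on assumed background rates and on whether Stage 1 is treated as binding. This is an error of labelling and reporting in the design tables. It does not show that the sample size fails its stated limits, and it does not touch the primary safety analysis.

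**What to change.** In both tables:

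1. Print the final rule for the pancreatic row: at least 1 response.
2. Exempt the row from the 15% FPR footnote and say that its attained FPR is 0 because the null is 0%.
3. Print its operating characteristics and name the assumption. With Stage 1 followed: power 91.3% at 15%, and 14.0%, 26.1% and 53.7% chance of passing at 1%, 2% and 5%. If all 17 are enrolled regardless: 93.7%, and 15.7%, 29.1% and 58.2%.
4. Say that subjects 16 and 17 do not decide efficacy when Stage 1 is followed, and that they add safety, PK, PD and precision.

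Change 21 to 36 into 17 to 36 in the protocol synopsis (Study Design, Phase 2: Cohort expansion, Number of Subjects), Protocol 6.1 and 6.1.3, and SAP section 3.

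The cost is wording. No subject numbers change, the totals of 184 and 188 stand, and the cohort need not end at 15. The price is that the row will look less rigorous than it now does.
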